7.5.2.3 Postponement of cures, modification of administration and reason for modification

- The number and percentage of patients with at least one deferred treatment and the reasons for these deferrals

- The number of patients with at least one dose change will be described by treatment type. Causes of dose changes will be presented. A listing of others will be provided.
- The number and percentage of patients who permanently discontinued protocol treatment and the causes of discontinuation will be described.

All parameters will be described according to the usual descriptive statistics.

7.5.2.4 Subsequent line

- The number of patients who received a subsequent line and subsequent patterns will be described.
- The number of patients who received a new HEC and the number of subsequent HECs will be described. A listing of the products used to load the beads will be provided.

All parameters will be described according to the usual descriptive statistics.

7.5.3 Toxici

Toxicities during treatment will be described according to NCI-CTC version 4.0 criteria by:

- The number of patients and toxicities by maximum grade and type;
- The number and percentage of patients with at least one toxicity across all courses by grade;
- The number and percentage of patients with at least one maximum grade 3-4-5 toxicity over all courses or at least one maximum grade 1-2 toxicity;

7.5.4 E.I.G

A summary of the SAEs will be provided by pharmacovigilance.

7.6 Exploratory Analyses

7.6.1 Definition

The exploratory analysis focuses on the search for factors predictive of progression-free survival and/or overall survival.

Progression-free survival is defined as the time interval from the date of inclusion to the date of 1^{ère} radiological progression or the date of death (from any cause). Patients alive and progression-free will be censored at the date of last report.

Overall survival is defined as the time interval between the date of inclusion and the date of death (regardless of cause). Patients lost to follow-up or alive at the time of analysis will be censored at the date of last report.

The variables for which the p-value is lower than 0.10 in univariate analysis or judged clinically relevant among the list to be defined will be retained for the multivariate analysis.

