4.3 Justification of the number of subjects needed

A 1-step Fleming design was used, with a one-sided α risk of 5% and a power ($1-\beta$) of 90%.

The clinical assumptions made were:

H_0 : A 55% progression-free live proportion during the first 9 months is unattractive;

H_1 : A proportion of patients alive without progression of more than 55% during the first 9 months would show the interest of the treatment; a proportion of 75% is hoped for.

48 evaluable patients were required. Taking into account a 20% rate of patients lost to follow-up or not evaluable, 58 patients were to be included.

The decision rules are as follows: of the 48 evaluable patients

- If 32 or fewer patients are alive without progression, then the treatment is considered ineffective
- If 33 or more patients are alive without progression, then the treatment is considered effective

The decision rule will be adjusted based on the actual number of evaluable patients.

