6.5 Statistics

The confidence intervals provided will be two-sided 95% confidence intervals except for the primary endpoint where the calculated confidence interval will be a one-sided 95% confidence interval.

Quantitative data will be described using the following descriptive statistics: number, mean, standard deviation, median, first and third quartile, and minimum and maximum. These statistics will be considered the usual statistics for the analysis of quantitative variables. Quantitative variables can be categorized using their median or a cut-off known from the medical literature.

Categorical variables will be summarized, using the following descriptive statistics: the number, frequencies and percentages for each level of the variable. These statistics will be considered as the usual statistics for the analysis of categorical variables.

When necessary, the 95% confidence intervals for the proportions can be calculated from the exact binomial distribution.

Survival data will be estimated and plotted using the Kaplan Meier method (Kaplan and Meier, 1958). They will be described by the median and rates calculated at different time points with their two-sided 95% confidence intervals. The confidence intervals for the rates will be constructed from the Greenwood variance calculated using the log-log transformation.

The median follow-up time will be estimated by the reverse Kaplan-Meier method (Shemper, 1996).

As an exploratory measure, for the uni and multivariate analyses, the hazard ratios will be estimated using a Cox model (Cox, 1984). The hypothesis of proportionality of the rates will be tested using the graphical representation and the test based on Schöenfeld's residuals (Grambsch, 1994); the linearity of the effect of the continuous variables on the risk will be evaluated from the graphical representation of the martingale residuals. Confidence intervals for the coefficient estimates of the Cox models will be calculated using the Wald method.

7 Statistical analysis

	Population ITT	Population ITTm	Tolerance population	Population Per protocol
Description of Baseline				
Eligibility criteria for inclusion	X	X		X
Demographic characteristics	X	X		X
Clinical characteristics at inclusion	X	X		X
Biological characteristics at inclusion	X	X		X
Characteristics related to the disease	X	X		X
Median follow-up time	X	X		X
Main criterion				
Progression-free survival rate at 9 months	X	X		X
Secondary criteria				

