7.6.2 Evaluation

For univariate and multivariate analyses, hazard ratios will be estimated using a Cox model (Cox, 1984). The proportionality of the rates will be tested using the graphical representation and the test based on Schöenfeld's residuals (Grambsch, 1994); the linearity of the effect of the continuous variables on the risk will be assessed from the graphical representation of the martingale residuals. Confidence intervals for the coefficient estimates of the Cox models will be calculated using the Wald method.

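### Exploratory Cox models: selecting factors at univariate p<0.10 leaves the Wald 95% intervals of null factors that enter this way below nominal coverage, and the optional median split costs power

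*SAP*

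**What the plan says.** SAP 7.6.1 searches for factors associated with progression-free and/or overall survival. The multivariable model takes "The variables for which the p-value is lower than 0.10 in univariate analysis or judged clinically relevant among the list to be defined". So there are two routes in, a p-value or clinical judgement, and the list behind the second has not been written. SAP 7.6.2 states: "Confidence intervals for the coefficient estimates of the Cox models will be calculated using the Wald method". SAP 6.5 sets the level: "The confidence intervals provided will be two-sided 95% confidence intervals except for the primary endpoint".

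On quantitative variables, the descriptive part of SAP 6.5 says: "Quantitative variables can be categorized using their median or a cut-off known from the medical literature". For the Cox models, however, 7.6.2 plans that "the linearity of the effect of the continuous variables on the risk will be assessed from the graphical representation of the martingale residuals", which presupposes covariates kept continuous.

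SAP 6.5 gives the status of the work: "As an exploratory measure, for the uni and multivariate analyses, the hazard ratios will be estimated using a Cox model". The table in SAP section 7 runs it in the ITT, modified ITT and per-protocol populations. The SAP gives no number of candidates, expected events, limit on model size, internal validation or warning about selection.

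**The concern.** A variable that enters because its p-value was below 0.10 has, by construction, an estimate some distance from zero in these patients. A Wald interval computed afterwards in the same patients ignores this. The fault is mainly an off-centre estimate, not a narrow interval. A null factor that gets in therefore has an interval that excludes a hazard ratio of 1 more often than the 95% label implies.

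Separately, cutting a variable such as CEA, CA 19-9, alkaline phosphatase or age at the sample median discards information and ties the cut to this sample.

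At stake is how far a reader can trust the reported factors, which may be carried forward as leads for later trials.

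**Working it through.** **Inputs from the documents.** SAP 4.3: 48 evaluable patients, and "58 patients were to be included" (48 × 1.2 = 57.6, rounded up to 58). Entry threshold 0.10 (7.6.1); two-sided 95% Wald intervals (6.5, 7.6.2). The plan gives no operating figure for the exploratory models, so there is none to reproduce.

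**Assumptions.** 5 to 20 candidates. Exponential times in 58 patients, with either 52 events (10% censored) or about 48 events (median PFS 10 months, follow-up 18 to 36 months). Simulation error on coverage is about 1 to 1.5 points.

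**1. Coverage for one null factor, analytically.** Entry needs |Z| > 1.645; the interval covers a hazard ratio of 1 if |Z| < 1.96.

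P(covers | entered) = (0.10 − 0.05) / 0.10 = 50%.

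**2. Coverage by simulation** (univariate screen at p<0.10, then a joint Cox model with Wald 95% intervals), for null factors that enter:

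| Setting | Coverage |
|---|---|
| All null, independent, 52 events: 5 / 10 / 20 candidates | 50% / 54% / 57% |
| All null, independent, about 48 events: 5 / 12 / 20 candidates | 54% / 55% / 56% |
| All null, independent, 10 candidates, 29 events | 52% |
| One real factor among 10, independent, HR 1.5 / 2.0 per SD | 60% / 70% |
| 10 nulls, mutual correlation 0.3 | 70% |
| Real factors present, correlation 0.2 to 0.3 | 85-95% |

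The last row is higher because a null factor correlated with a real one often enters through a genuine univariate association, which the joint model then adjusts away.

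**3. Does the screen raise the chance of a false factor?** All candidates null and independent, about 48 events, chance that at least one interval excludes 1:

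| Candidates | Screened | All fitted, no screen |
|---|---|---|
| 5 | 21-23% | 27-28% |
| 12 | 43% | 62-64% |
| 20 | 57-59% | 87-89% |

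At an equal number of candidates the screen lowers this chance. A fall in false factors must come from naming fewer of them.

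**4. Median split.** For a normal covariate, the efficiency of a split at the median is 2/π = 0.64, a loss of 1 − 2/π = 36%. Simulated power for a single factor (58 patients, about 48 events, two-sided 5%):

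| Log HR per SD | Continuous | Median split | Loss |
|---|---|---|---|
| 0.3 | 51% | 35% | 16 points |
| 0.4 | 74% | 52% | 22 points |
| 0.5 | 90% | 71% | 19 points |

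At HR 2 per SD with 52 events, the approximate formula Φ(√(d·e)·log HR − 1.645), with d events and efficiency e, puts the chance of passing the 0.10 screen at over 99% continuous and 99% split. The loss there is negligible.

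**5. The alternative.** A prespecified model, continuous covariates, no screen, 52 events: coverage for null factors is 93-94% with 5 factors and about 91% with 10. Power for one real factor of HR 1.5 per SD in the 5-factor model is 76%. With 5 null factors, the chance of at least one false factor is still about 26-29%.

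**The case against.** The strongest reply is that the analysis is labelled exploratory and bears on neither the 33-of-48 decision rule nor any secondary endpoint. That stands, and it limits the matter to how the factor results are reported. It does not make an interval labelled 95% accurate.

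Four stronger readings are tempting, and the documents do not support them:

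- A reader might take coverage of about 54% as a property of this SAP. It belongs to independent, all-null candidates. Clinical covariates such as CEA, CA 19-9 and alkaline phosphatase are unlikely to be independent, and with real, correlated factors coverage may be 85-95%. It also does not describe variables entered by the second route, "judged clinically relevant among the list to be defined".
- A reader might count the baseline variables in SAP 7.1 as roughly 20 Cox candidates. That section lists variables to be described and does not call them candidates.
- A reader might conclude that real continuous effects are missed. The split is permitted, not required; the permission sits among the descriptive statistics; and linearity checks are planned. If it is used, real effects are detected less often.
- A reader might blame the screen for a high rate of false factors, or call the results largely selection noise. At an equal number of candidates the screen lowers that rate, and the second claim needs nearly all candidates to be null, which the documents do not say.

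**Conclusion.** The point holds as a cheap improvement to the exploratory analysis. For null factors entering through p<0.10, the planned 95% intervals cover about 50-57% of the time if all candidates are null and independent, up to about 70% in other settings with nulls unrelated to real factors, and about 85-95% when nulls are correlated with real factors. All of this rests on an assumed 5 to 20 candidates and an assumed number of events. The modified ITT set (48 planned) and the per-protocol set may offer fewer patients than the 58 used here.

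A median split, if carried into the Cox models, costs about 36% of the information for a normal covariate and 16-22 points of power at log hazard ratios of 0.3-0.5 per SD. The primary decision is unaffected.

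**What to change.** 1. In SAP 6.5 and 7.6, keep quantitative covariates continuous in Cox models: log scale for CEA and CA 19-9, and a spline or transform if the planned martingale plot shows non-linearity. Use median categories for description only.
2. In SAP 7.6.1, replace the p<0.10 rule with a short list, about five factors for the expected events, fixed before database freeze, fitted together and all reported. The list has to be written anyway, and SAP 4.5 already sets database freeze as the limit for changes to the plan. Choose factors with near-complete data and adequate variation. KRAS needs care: Protocol III does not require it routinely at inclusion, and SAP 6.3 does not replace missing values, so forcing it in could drop patients. The Köhne score may vary little, since Protocol II.1 excludes extra-hepatic disease other than up to three small lung nodules.
3. If screening is kept, bootstrap the whole selection procedure, and label the Wald intervals as unadjusted for selection.

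The cost is SAP wording and slightly more programming, with no added patients, visits or data. The downside is a less flexible factor search and hazard ratios per unit instead of high/low groups. The change brings per-factor coverage close to nominal but does not control multiplicity: the 26-29% chance of some false factor among five nulls remains and should be stated with the results.

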7.6.2 Evaluation

For univariate and multivariate analyses, hazard ratios will be estimated using a Cox model (Cox, 1984). The proportionality of the rates will be tested using the graphical representation and the test based on Schöenfeld's residuals (Grambsch, 1994); the linearity of the effect of the continuous variables on the risk will be assessed from the graphical representation of the martingale residuals. Confidence intervals for the coefficient estimates of the Cox models will be calculated using the Wald method.
